# I. Study Summary Synopsis

Title	Kidney C oordinated H e A lth M anagement P artnership (Kidney CHAMP) trial		
Short Title	K CHAMP Trial		
Study Description	This is a randomized clinical trial to test the effectiveness of a multifaceted EHR-based PHM intervention to improve evidence-based CKD care in high-risk patients		
Objectives	Primary Objective To perform a 42-month pragmatic, cluster RCT comparing the effect of an EHR-based PHM intervention versus usual care on key processes of care in 1,650 high-risk CKD patients.  Aim 1a: To examine the effect of the intervention on systolic blood pressure (SBP) in HTN patients.  Aim 1b: To examine the effect of the intervention on RAASi use in albuminuric patients.  Aim 1c: To examine the effect of the intervention on exposures to potentially unsafe medications.		
	Secondary Objective To test the clinical effectiveness of a multifaceted PHM intervention in reducing kidney disease progression in 1,700 high-risk CKD patients enrolled in a 42-month pragmatic, cluster RCT		
Primary Outcome	≥40% decline in estimated glomerular filtration rate (eGFR) or end stage kidney disease		
Secondary Outcomes	
 
blood pressure control
 
renin-angiotensin aldosterone system inhibitors use
 
exposure to potentially unsafe medications
 
		
Study Population	1,650 high-risk CKD patients not presently seeing a nephrologist		
Phase or Trial Type	Effectiveness		
Description of Sites/Facilities Enrolling Participants	100 University of Pittsburgh Medical Center (UPMC)-affiliated PCP practices located across southwest Pennsylvania University of Pittsburgh; University of Pennsylvania		
Description of Study	Intervention bundle includes nephrology electronic consults, pharmacist-led medication reviews and nurse-led CKD education		
Intervention	Usual Care: per PCP as routine		

Study Duration	42 months
Participant Duration	24 months

### II. Introduction

CKD is associated with an unacceptably high human and financial cost. Over 12 million US adults have CKD stage 3-5.6 As the population ages and diabetes (DM), HTN, and obesity rates increase, the prevalence of CKD will grow. 6 Kidney disease is the 9th leading cause of death and attributable Medicare expenditures are \$80 billion. Over 1/3rd of this is spent on ESRD patients, who represent < 5% of patients with CKD.

The overwhelming burden of CKD care falls to PCPs. PCPs deliver most care to patients with non-dialysis dependent CKD due to its growing prevalence and the relative dearth of nephrologists. 10-12,50-52 However, PCPs report that limited CKD knowledge, time constraints, complex case-mix, and inadequate system-based resources contribute to gaps in CKD care. 12,14,15,17,38,51,53 These gaps include poor patient education, 16 inadequate diagnostic evaluation, 12,27,38,54 suboptimal treatment of HTN and use of RAASi in albuminuric patients, 19,23,55-57 inappropriate medications or dosages, 21,58-61 and late referrals of high-risk patients. 13,19,20 These shortcomings inevitably lead to increased CKD progression, hospitalizations, and mortality. 20,25,26,62-64

Novel system-based interventions are needed. The above observations underscore an urgent need for system-based interventions to improve CKD care and outcomes. We recently conducted a national survey and found the overwhelming majority of PCPs endorse systematic interventions to improve CKD care. 14 One potentially high-impact, low-cost intervention that has improved outcomes in other chronic diseases is EHR- based PHM. 65,66 CKD is an ideal setting to evaluate the impact of EHR-based PHM due to the: 1) high prevalence of disease, 2) ability to detect high-risk disease with widely used biomarkers (i.e., creatinine/eGFR, change in eGFR, urine albuminuria), 3) baseline gaps in care that provide opportunities for improvement, and 4) patient benefit and health system savings conferred by avoiding or delaying catastrophic outcomes (e.g., ESRD). 19,31,67 National primary care organizations have called for the use of EHR-based PHM in primary care and a recent NIDDK conference advocated for urgent research examining the effectiveness of CKD PHM.68

A conceptual model. A conceptual model of care provides an approach to examine care deficiencies. Disease management consists of 7 simplified steps 4. GOAL

(**Figure 1**). At each step, the potential for lapses in care exists. Leveraging IT tools to risk stratify patients, deliver decision support, and to provide electronic guidance with specific recommendations overcomes barriers at nearly each step by providing timely cognitive support to aid risk assessment, diagnostic evaluation, and treatment selection while lowering the burden on PCPs. However, studies are needed to test the feasibility and effectiveness of these strategies in improving CKD outcomes.

[figure not shown]

Fig 1. A Conceptual Model for CKD Management

Improving alignment between patient risk and treatment intensity. PCPs struggle to recognize high-risk patients early in their course.  In the US, 2/3rds of incident dialysis patients have less than 1 year of nephrology care before initiating dialysis, leading to greater morbidity and mortality.  However, fewer than 1/3rd of non-dialysis dependent CKD patients with an eGFR< 60 are at high risk for poor outcomes.  Given the scarcity of nephrologists, a vital need exists for tools to effectively risk stratify the CKD population and improve the efficiency of resource allocation.  This study identifies high-risk patients earlier in their disease course, when outcome trajectories can be improved.

Actionable strategies to improve CKD care and outcomes in high-risk disease. Key evidence-based process of care targets in CKD are improved: 1) HTN control, 19,44,55,56 2) RAASi use in proteinuric CKD, 23,57 3) avoidance of inappropriate medications or dosages, 21,58-61 and 4) timely nephrology referrals in high-risk CKD. 13,19,20 These strategies have been demonstrated to slow CKD progression, prevent ESRD, decrease hospitalizations, and improve patient safety. 13,19-21,23,55-61 Several approaches have been shown to enhance adoption of these critical processes of care: a) electronically delivered expert guidance by nephrologists, 13,77 which slowed CKD progression, b) pharmacist led medication reconciliation, 43,78-80 which decreased medication related problems, and c) patient education, 56,57 which increased patient engagement and self- management. 81,82 However, large pragmatic studies validating the effectiveness of these interventions are lacking.

Summary and Implications: Combining complementary interventions in a highly pragmatic, cluster RCT of EHR-based PHM for high-risk CKD patients could establish a novel, exportable strategy to improve patient care, safety, and outcomes (**Figure 2**). Our multifaceted intervention will improve CKD risk stratification, resource allocation, adoption of evidence-based interventions, and patient medication safety. The intervention may thereby improve CKD outcomes and transform approaches to CKD care. Further, the study will deliver templates, algorithms, and code to enable dissemination to other settings.

[figure not shown]

Figure 2. PHM to improve CKD care

# III. Study Objectives

The overarching aim of the Kidney Coordinated HeAlth Management Partnership (Kidney CHAMP) trial is to test the effectiveness of a multifaceted EHR-based PHM intervention to improve evidence-based CKD care in high-risk patients in a highly pragmatic, cluster randomized trial (CRT). By combining timely nephrology guidance, pharmacist-led medication management services, and CKD patient education, our intervention will improve CKD risk stratification, resource allocation, adoption of evidence-based interventions, and medication safety and efficacy, while minimizing the PCP and patient burden

Aim 1: To perform a 42-month pragmatic, cluster RCT comparing the effect of an EHR-based PHM intervention versus usual care on key processes of care in 1,700 high-risk CKD patients.

Aim 1a: To examine the effect of the intervention on systolic blood pressure (SBP) in HTN patients.

Aim 1b: To examine the effect of the intervention on RAASi use in albuminuric patients. Aim 1c: To examine the effect of the intervention on exposures to potentially unsafe medications.

Aim 2: To test the clinical effectiveness of a multifaceted PHM intervention in reducing kidney disease progression in 1,700 high-risk CKD patients enrolled in a 42-month pragmatic, cluster RCT.

### IV. Study Design

Study design. A 42-month cluster RCT with randomization occurring at the practice level (to minimize contamination) and stratified by number of high-risk CKD patients in the practice. All 90 practices will be randomized. Patient enrollment will continue for 18 months, with a minimum of 24 months of follow-up (**Fig 3**).

[figure not shown]

Figure 3. Flow diagram of cluster RCT of EHR-based PHM.

PCP primary care provider, PHM population health management, KFRE kidney failure risk equation, CA cancer

Population and Setting. The study leverages a PCP network that includes 90 practices; 330 PCPs; and over 480,000 patients to conduct a cluster RCT testing the effectiveness of an EHR-based CKD PHM intervention. In this pragmatic study, practices will be randomized to the intervention. Secondarily, their high- risk CKD patients who are not seeing a nephrologist will be enrolled.

Eligibility. Inclusion criteria are (**Figure 3**): a) age  $\geq$  18 and  $\leq$ 85, b) most recent eGFR < 60 ml/min/yr,c) UPMC health plan insurance, d) established care with UPMC PCP, e) high-risk CKD (see **Table 1**). Exclusion criteria are: a) history of kidney transplant, b) receiving maintenance dialysis, c) recent (within 12 months) outpatient nephrology visit, d) baseline eGFR  $\leq$  15ml/min, or e) expected survival  $\leq$  6 months/hospice.We will use the validated 4- variable KFRE to estimate 5-year ESRD risk. We will supplement these criteria by including other patients who are high risk for poor outcomes (**Table 1**).

Table 1: High risk CKD

### eGFR 15-29ml/min OR

5 year risk of ESRD  $\geq$  4% determined using the validated 4-variable kidney failure risk equation (urine dipstick substituted for ACR when necessary) OR

Rapid decline in eGFR operationalized as annualized eGFR decline >=5ml/min/yr74\*

\*determined from 2 eGFR values at least 12 months apart

### PCP Recruitment and Engagement.

Before implementation at each site, we will provide a remote/on-site presentation during a scheduled practice meeting. Communication with lead physicians will continue during the study at least biannually by teleconference or on-site lunches to discuss feedback and concerns and document comments on a standardized feedback form. Study/Site PIs will also meet with practice physicians as needed to address concerns. We will anonymously survey intervention arm PCPs every 6 months to assess their experience with the intervention bundle. This will include: ease of use, questions communicated by patients, effects on patient medication use and adherence, utility of the recommendations, and temporal burden of the intervention. Minor adjustments to PHM intervention workflow will be made as needed to ensure continued workflow optimization.

[figure not shown]
Randomization. The unit of randomization will be the practice (**Fig. 3**), stratified by estimated number of eligible CKD patients within the practice (small [<15 patients], medium/large [≥15 patients]). Randomization will use a computer generated random number sequence with random block sizes of 4 and 6.

CKD Registry and PHM Dashboard. Our CKD registry includes all outpatients with a recent eGFR < 60 ml/min followed by a UPMC PCP. The CKD registry identifies patients with CKD, phenotypically characterizes them, and stores information on labs, medications of interest, upcoming PCP appointments, and information about CKD outreach (including dates of electronic outreach, medication reviews, patient education, and pending labs/studies). The registry is updated automatically with activity in the patient chart.

Dashboards are medical informatics data representations that can be employed when decisions need to be made about a population of patients. These tools display groups of patients based on clinical characteristics and allow providers to stratify, filter, and sort by relevant variables. Thus, subgroups of patients can be rapidly identified and targeted for more intensive therapy. Dashboards can improve evidence-based care; however, they have been slow to enter clinical

practice because of the sophisticated underlying data requirements.84,93

Our CKD PHM dashboard (**Figure 4**) includes population-based reports built off of the registry (e.g., high-risk patients with PCP appointment in October), as well as graphical and tabular displays of key metrics (e.g.,identified subpopulation with albuminuria who are not on RAASi). Population reports accessible through the dashboard will allow the study coordinator to sort patients based on phenotypic data and upcoming PCP appointments, and include filters such as CKD stage, RAASi use, and PCP group. Longitudinal tracking and notation functions interface with the dashboard and allow documentation of study inclusion, and dates of scheduled/completed aspects of the intervention. Dashboard reports will allow the coordinator to rapidly flag patients for urgent concerns, send routine reminders to PCPs to implement recommended interventions, ensure follow-up on pending components of the intervention, and actively monitor follow-up status. Dashboard reports will be actionable and will allow the manager to view more detailed information in a viewing pane without leaving the report. The reports allow the coordinator to jump directly into activities to communicate with the patient, the patient's PCP, and the respective nephrologist or pharmacist.

Patient screening and enrollment. Each month, the coordinator will use the CKD PHM tool to review high-risk patients with an upcoming (within 1 month) appointment with their PCP to determine eligibility. Possible decisions will include actively enroll, permanently exclude, or not presently eligible but may rescreen if deemed high-risk at next PCP appointment. Once delineated, the patient's status is noted in the EHR with a modifiable study flag not visible to providers, but that is continually tracked, updated, and ascertained through the PHM dashboard.

For intervention patients, the coordinator will send a scripted EHR message with associated decision support to the PCP about 1-3 weeks prior to their scheduled PCP appointment. When the PCP accepts the decision support recommendations for an electronic nephrology consultation, a medication reconciliation and safety review, and standardized patient

education, the orders will be placed . Patients enrolled to practices randomized to usual care will receive care as they currently do.

A study coordinator is needed to screen patients for eligibility to ensure identical enrollment criteria are used in the intervention and usual care arms. Because coordinators will review recent patient documentation for potential enrollees in the intervention arm, they will note if a patient has a terminal condition, etc. However, this information may only be recorded in the text portion of documents. Hence, we will use a standardized form to screen patients in both arms to ensure comparable enrollment. To minimize potential bias from the nurse coordinator's non-blinded status, a local PI blinded to PCP group assignment will review randomly selected screened patients on a weekly basis to ensure accurate implementation of the eligibility criteria. Potential discrepancies will be resolved by consensus and further training as necessary.

Intervention. Approximately 1-3 weeks prior to an appointment, PCPs of enrolled patients will receive an EHR message informing them of the patient's high-risk CKD status. Linked with the notification is a decision support alert (Figure 5) that asks the provider to a) order a CKD care bundle that includes an electronic nephrology consultation, pharmacist led medication reconciliation and safety review, and a CKD education session, or b) order a traditional nephrology consult, or c) provide a reason why neither choice is warranted. Notification messages and PCPs' responses will be documented in the EHR.

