Sample Size: We base our sample size justifications on computational techniques that match our study design and proposed analytical approach within the constraints of published methodologies (PASS 13 Power Analysis and Sample Size Software (2014). NCSS, LLC. Kaysville, Utah, USA). We selected our sample size to attain adequate power to assess differences in the primary outcome using the design effect method for time-to-event approach.(3) We assumed two-sided tests at  $\alpha = 0.05$ , an Intra-Class Correlation (ICC) of 0.01 (as recommended for health services research when no preliminary data on ICC are available)(4), a cluster size of 19 patients per practice, and an 18-month enrollment period with an additional follow-up of 24 months after the accrual period. For an individually randomized trial, a total sample size of 1,102 provides at least 80% power to detect a hazard ratio of 0.64 (or a 0.05 difference in event proportions) assuming the control event proportion at 24 months is 0.15, based on our preliminary data. Accounting for the clustered design and 20% attrition (e.g., patients leaving the health system), the required sample size is 1,653.

For the secondary outcome (BP in patients with HTN and total person-time of medication exposures), this sample size achieves at least 80% power to detect a small effect size, standardized mean difference of at least 0.2. In the 96% of the cohort estimated to have a diagnosis of HTN, this is equivalent to detecting a mean SBP difference of 3mmHg (based on preliminary data with SBP standard deviation [SD] = 15mmHg), a mean RAASi use difference of ~78 person-years (modeled SD = 390 person-years, based on simulation), a mean medication use exposure difference of 72 person-years (modeled SD= 360 person-years based on simulation).

**Preliminary Analyses:** Preliminary analyses will focus on data checks for completeness and accuracy and address any issues with data quality. Descriptive summaries will be examined overall and by intervention group and time point. We will compare distributions of baseline characteristics for practices and patients between randomized groups to assess the effectiveness of randomization. All primary analyses for intervention group comparisons will use an intention-to-treat approach and results will be reported using the CONSORT extension to cluster RCTs.(5) We will adjust for statistical or clinical differences in secondary analyses.

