**General Approach**: We will use linear mixed models (LMM) or generalized LMM (GLMM) to account for clustering. These models will include random practice intercepts to account for correlation of observations from patients within the same practice. For analysis involving repeated measurements, random patient intercepts nested within practice effects will also be included. Unadjusted models will test a fixed intervention effect; adjusted models will include stratification variable used in randomization (practice size) and patient characteristics (age, sex, race, baseline levels). All statistical analyses will be performed in R using glmmTMB and lme4 packages to fit discrete-time survival models, GLMM, and

LMM and use the marginal effects package to estimate adjusted average responses and contrasts.

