Primary clinical outcome (Aim 2: eGFR decline ≥40% or ESRD): Our primary analysis will use discretetime survival methods to examine the occurrence of the composite endpoint at 6-month intervals from baseline. To determine progression at each of these discrete time points, the average of all eGFR measurements within a +/- 3-month window will be used in order to account for random eGFR fluctuations and potential ascertainment bias. We will employ generalized GLMM with complementary log-log link with random practice intercepts to account for practice-level clustering. This is analogous to a Cox model with frailty for continuous-time survival data (i.e., a random effects survival analysis model). The unadjusted model will include fixed effects for intervention, and time. The functional form of time (categorical or continuous with restricted cubic splines) will be selected based on the Akaike Information Criteria (AIC). Adjusted models will include pre-specified patient (age, sex, race, baseline eGFR) and practice variables (practice size). MMWD, being moved to hospice care, or mortality will be treated as competing events. Those that did not reach any endpoint will be censored at the end of study (July 31, 2022). In secondary analysis, we will use eGFR as a continuous variable and include random patient intercepts nested within random practice intercepts. The unadjusted model included fixed effects for intervention, time, and treatment by time interaction. We will compare the rate of eGFR decline over time between groups. As sensitivity analyses, we evaluated a) smoothing-spline mixedeffects models since eGFR trajectories may be nonlinear, and b) requiring 2 consecutive eGFR values below the 40% decline/ESKD threshold.

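### The primary-outcome model labelled unadjusted omits the randomisation stratum, and the SAP does not say which model carries the primary test; if practice size is prognostic, the stratum-free test is mildly conservative

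*Combined protocol and SAP*

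**What the plan says.** **Design.** The protocol (Randomization paragraph under PCP Recruitment and Engagement) randomises practices "stratified by estimated number of eligible CKD patients within the practice (small [<15 patients], medium/large [≥15 patients"). Within strata, "Randomization will use a computer generated random number sequence with random block sizes of 4 and 6". Study Design adds: "All 90 practices will be randomized".

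**Primary analysis.** The final SAP, Primary clinical outcome, fits a discrete-time complementary log-log mixed model with a random practice intercept. Two versions are given:
- Unadjusted: "The unadjusted model will include fixed effects for intervention, and time".
- Adjusted: the same, with age, sex, race, baseline eGFR and practice size added.

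General Approach sets the rule for all outcomes: "Unadjusted models will test a fixed intervention effect; adjusted models will include stratification variable used in randomization (practice size") and patient characteristics.

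**Which version is primary.** This is not stated. The General Approach sentence just quoted attaches the test of the intervention effect to the unadjusted models. Preliminary Analyses says: "We will adjust for statistical or clinical differences in secondary analyses". Both lean towards the unadjusted model. Pointing the other way, the Summary of Major Revisions presents the pre-specified covariates as a way to gain efficiency.

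**Other outcomes.** Under Secondary process of care outcomes, the blood pressure models are adjusted for practice size. The linear mixed model for medication exposure days is described only with a random practice effect. The sentence on further covariates follows the count models and mentions their offset, so it is unclear whether it also covers the linear model.

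**The concern.** Stratified randomisation balances the arms within each stratum. If outcome risk differs between small and larger practices, that difference therefore drops out of the true sampling error of the treatment effect. A model without the stratum does not know this. It assigns the between-stratum difference to the practice random-intercept variance and so reports a standard error larger than the real one. The confidence interval is then too wide, the true type I error is below the nominal 0.05, and some available power goes unused.

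The second issue is specification. Two models for one primary outcome, one following the randomisation and one not, with neither named as primary, leave open which p-value is the trial's result. The Summary of Major Revisions records SAP changes made after results were first disclosed to the team in March 2023, so this is not a choice to leave implicit.

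**Working it through.** **Inputs from the final SAP, Sample Size.** "We assumed two-sided tests at" alpha 0.05; "an Intra-Class Correlation (ICC) of 0.01"; 19 patients per practice; 1,102 patients for an individually randomised trial at 80% power or more; hazard ratio 0.64; control event proportion 0.15 at 24 months; 20% attrition; final size 1,653.

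**Assumption.** The share *f* of between-practice variance explained by the stratum is not in the documents. It is varied from 0 to 1.

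**Step 1: reproduce 1,653.** Design effect = 1 + (19 − 1) × 0.01 = 1.18.
- Plain formula: 1,102 × 1.18 / 0.80 = 1,626, within 2% of the stated figure.
- Whole practices: 1,102 × 1.18 / 19 = 68.4, rounded up to 69; 69 / 0.80 = 86.25, rounded up to 87; 87 × 19 = 1,653.
- A design effect rounded to 1.2 also works: 1,102 × 1.2 / 0.80 = 1,653.

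Every route uses at least the full design effect. None takes credit for stratification.

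**Step 2: effect of leaving the stratum out.** With the stratum in the model, the residual design effect is 1 + 0.18 × (1 − *f*).
- Standard-error ratio, without over with: r = √(1.18 / [1 + 0.18(1 − *f*)]).
- True alpha of the stratum-free test: 2 × [1 − Φ(1.96 r)].
- Power with the stratum, starting from 80% without it: Φ(2.80 r − 1.96), where 2.80 = 1.96 + 0.84.

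| *f* | r | True alpha without stratum | Power with stratum |
|---|---|---|---|
| 0 | 1.000 | 0.050 | 80.0% |
| 0.10 | 1.008 | 0.048 | 80.6% |
| 0.25 | 1.020 | 0.046 | 81.5% |
| 0.50 | 1.041 | 0.041 | 83.0% |
| 1 (ceiling) | 1.086 | 0.033 | 86.1% |

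The power column is compared with a nominal 80%. Because the true sampling error is smaller than the stratum-free model reports, that model's own power is Φ(0.84 r): 80.5% at *f* = 0.25 and 80.9% at *f* = 0.50. The net gain is then about 1.0 and 2.1 points, the lower part of the 1 to 3 point range.

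**Step 3: what size of risk gap gives these shares?** Take an overall risk of 0.125, the mean of 0.15 and 0.10, and let small practices hold an assumed share w of 15% to 50% of patients. Then *f* = w(1 − w) × gap² / (0.01 × 0.125 × 0.875).
- Gap of 1 to 3 percentage points: *f* = 0.01 to 0.21, so r is below 1.02 and the power gain is about 1 point or less.
- Gap of 5 points: *f* = 0.29 to 0.57.
- *f* = 1 needs a gap of about 7 to 9 points.

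**Step 4: simulation of the planned model type.** Complementary log-log model with random practice intercept, 87 practices, 300 runs per scenario. For stratum log-hazard gaps from 0 to 0.5, the mean standard-error ratio was 1.004 to 1.02. Power without and with the stratum was 83.7% and 83.7% at gap 0, and 85.7% and 86.0% at gap 0.5. Under the null at gap 0.5 both models rejected in 3.3% of runs; the Monte Carlo error there is about 1 point, too coarse to separate the alphas in Step 2.

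**The case against.** The strongest reply is that the stratum is already handled. Practice size is in the pre-specified adjusted primary model and in the blood pressure models. The sentence that puts adjustment in secondary analyses follows the comparison of baseline characteristics, so it may concern observed imbalance only and not the pre-specified covariates. This stands in part: it cannot be said that the SAP's primary test omits the stratum, only that the SAP does not exclude that reading.

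Three stronger readings are tempting, and the documents do not support them.
- **That power bought by the design is lost.** Step 1 shows that 1,653 takes no credit for stratification. What may be forgone is extra precision, not the planned 80%.
- **That the loss is material.** A simulation with a small-versus-large hazard ratio of 2.0 gave about 80% against 85% power. That gap, added to a practice standard deviation of 0.25 on the log hazard, implies a total ICC of about 0.023 to 0.028, more than twice the SAP's value. At a hazard ratio of 1.5, power was 78% with either model. The SAP's ICC is itself a default chosen without preliminary data. At an assumed 0.03 the design effect is 1.54, and 25% to 50% explained gives r = √(1.54/1.405) = 1.05 to √(1.54/1.27) = 1.10. The documents do not support that ICC over 0.01.
- **That the eGFR slope test gains too.** That test is the treatment-by-time interaction, a within-patient contrast. A stratum main effect removes differences in level, not in slope. In simulated balanced repeated eGFRs with a 5-unit stratum gap, the interaction estimate was identical with and without the stratum, and its standard error was unchanged to about six decimals.

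**Conclusion.** The point holds in a limited form. One of the two primary-outcome models omits the factor by which practices were randomised, the SAP does not say which model is primary, and its wording leans towards the one without the stratum. If that model is used and practice size is prognostic, the test is conservative: at the SAP's ICC and cluster size, a standard error about 2% to 4% too large for an assumed 25% to 50% share, with a ceiling of about 9%. The documents contain no data linking practice size to progression; without such a link nothing is lost. Validity is not threatened, since any error in type I rate is downward. This is a low-cost improvement in precision and, more usefully, a gap in specification to close.

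**What to change.** 1. In the final SAP, Primary clinical outcome, list intervention, time and randomisation stratum as the fixed effects of the basic complementary log-log model, so that whichever version is primary contains the stratum.
2. State which of the two models carries the primary test.
3. Wherever the SAP says practice size (General Approach, Primary clinical outcome, Secondary process of care outcomes), define it as the <15 versus ≥15 stratum as estimated at randomisation, not the number of patients later enrolled.
4. State that the linear mixed model for medication exposure days also includes it. The blood pressure models already do, and on a fair reading so do the medication count models.
5. Add practice size to the covariate list in the Summary of Major Revisions. This is housekeeping; its absence from a change summary is not an error.

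No change is needed to the eGFR slope test on this account. The cost is one binary covariate, available from randomisation, and a few lines of SAP text, with no change to sample size or data collection. Because results were disclosed in March 2023, any wording added after that should be dated as such, and the results of both models reported.
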